The secondary efficacy objective is to evaluate whether administration of CAP-1002 by intracoronary infusion may result in other left ventricular structural or functional cardiac benefits for subjects with ischemic left ventricular dysfunction and a previous MI. Also evaluations will investigate whether administration of CAP-1002 may result in clinical or biomarker benefits for subjects with ischemic left ventricular dysfunction and a previous MI.

Study Design:

In Phase 2, the Primary Randomized Cohort will enroll up to approximately 103 subjects with a previous myocardial infarction (MI) and resultant ischemic left ventricular dysfunction meeting all inclusion and no exclusion criteria. The Primary Randomized Cohort will include the Recent and Chronic MI strata (n= approximately 51-52 per stratum). These 103 subjects will be randomized in a double-blind fashion to receive either CAP-1002 or placebo (collectively referred to as Investigational Product [IP]) in a 2:1 ratio favoring CAP-1002 to achieve up to 93 subjects with complete 12 month data (assumes 10% non-completion rate and 103 subjects randomized). After completion of the screening procedures and meeting all inclusion and exclusion criteria, study subjects will be randomized to receive CAP-1002 or placebo administered via intracoronary infusion. All subjects in the Primary Randomized Cohort will be followed at week 2 and at months 1, 3, 6 and 12 after planned CAP-1002 or placebo infusion. Efficacy will be assessed at all specified post-infusion visits, with the 12 month visit being the primary efficacy endpoint. An administrative interim analysis of the final 6 month data will be performed when all subjects in the Primary Randomized Cohort have completed the 6 month visit to assist in planning Phase III studies.

The double-blind, placebo-controlled design of the Primary Randomized Cohort will maximize

the study's ability to assess both safety and efficacy, as both may be subject to bias from the perspective of Investigators and subjects.

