When fully enrolled, the ALLSTAR study will include a total of up to approximately 134 subjects with ischemic left ventricular dysfunction and a previous MI. Of these, up to approximately 83 will be treated (infused) with CAP-1002 (n=14 Safety Cohort, n=69 Primary Randomized Cohort) and up to approximately 34 will receive placebo (Primary Randomized Cohort only). Up to 17 subjects may be enrolled into the Phase II Exploratory Randomized Cohort. However, since this group is exploratory in nature, enrollment of the Primary Randomized Cohort will define the end of the study; that is, once the Primary Randomized Cohort is fully enrolled, the study will be considered closed for further subject enrollment.

Test Product, Dose, and Mode of Administration:

[REDACTED]

[REDACTED]

[REDACTED]

Inclusion Criteria:

1. History of MI (STEMI or NSTEMI) within the prior 12 months due to a coronary artery event and evidenced by at least two of the following: typical ischemic symptoms, serial ST-T changes (new ST elevation or new left bundle block) and/or elevated troponin or CK-MB >5 times the upper limit of normal. Also at least one of the following: development of pathological Q wave ECG changes, imaging evidence of new loss of viable myocardium, or new regional wall motion abnormalities.
 - The following assessments will be permitted within 28 days immediately following the subject's MI: signing ICF, review of medical history, review of concomitant medications, and collection of laboratory samples required for assessment of study eligibility criteria (e.g., eGFR, HbA1c, hepatitis serology, HIV serology, LFTs, hematocrit, WBC, and platelet count). All other screening tests, including the subject's cardiac MRI and CT (chest, abdomen, pelvis), must be conducted greater than 28 days post-MI. *Infusion must occur within 28 days of the first screening procedure that is performed greater than 28 days post-MI.* Relevant safety laboratory sample collections (e.g., chemistry, hematology, urinalysis) may need to be repeated as they must be obtained within 28 days of the subject's infusion.
2. History of percutaneous coronary intervention (PCI), with stent placement resulting in TIMI flow = 3, in the coronary artery supplying the infarcted, dysfunctional territory and through which the treatment will be infused.

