7.3.5 Month 6 Visit (Day 180 ± 6 days) Procedures

Subjects will undergo multiple assessments 6 months after intracoronary infusion, including:

- Cardiac physical examination
- Medication review
- Adverse events assessment
- Vital signs
- 12-Lead ECG
- Laboratory tests: hematology, chemistry, urinalysis, DSA monitoring, serum NT-proBNP; refer to [Table 1](#) for comprehensive list of laboratory tests
- Serum for biomarkers (if subject has provided consent)

- Cardiac MRI
- 24 hour ambulatory ECG recording
- NYHA functional class assessment
- Six Minute Walk Test
- MLHFQ
- SF-36 health survey
- WPAI:SHP questionnaire
- Patient Global Assessment

If subjects undergo inter-current ICD/pacemaker placement, study imaging sites must be trained and certified specifically for this protocol prior to conducting cardiac MRI in subjects with ICD and/or pacemaker placement. If subjects develop MRI contraindications, a cardiac MRI will not be performed. Such subjects will continue to be followed in the study and undergo all 6 month study procedures except MRI. Any subject whose GFR declines to <30 mL/min during a given MRI study will not undergo contrast administration on this and subsequent MRI studies. Such treated subjects will not be withdrawn but will still be followed for inclusion in safety and efficacy analyses for other parameters assessed during the study.

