either Month 6 or Month 12 changes from baseline missing, but not both. Therefore, for analyses based on the mITT population, missing data will be addressed using ML. For analyses based on the ITT population, in which some subjects may have both Month 6 and Month 12 changes from baseline missing, multiple imputation will be used based on all observations and will use a fully conditional specification method with 20 burn-in iterations and the regression method of imputation. Variables in the imputer's model will be baseline observation (because baseline is used as a covariate in analyses), Month 6 change from baseline, Month 12 change from baseline, and treatment group. Because the MAR assumption is not testable, and because it seems possible that subjects with poorer outcome may be more likely to miss trial assessments, a sensitivity analysis under a "missing not at random" (MNAR) assumption will be done (for the final analysis only) of the primary efficacy endpoint in which multiple imputation will use the pattern-mixture model approach to address missing values; i.e., the imputation will be based on a pre-specified subset of subjects. For this MNAR analysis, only those subjects who had implantable cardioverter defibrillators (ICDs) inserted during the trial. Because very few missing observations are expected in this trial, 5 imputed data sets will be used for all analyses using multiple imputation.

A closed testing procedure will be used for the primary efficacy analysis only (see [Section 2.3.5](#)) and will be done as follows:

1. Let  $p_f$  and  $p_s$  be the p-values from the tests of the individual null hypotheses involving the full group and the subgroup, respectively; tests will be based on least squares (LS) means comparisons.
2. Let  $t_{max} = \max(t_f, t_s)$ , where  $t_f$  and  $t_s$  are the t-statistics from the full group and subgroup analyses in (1) above.
3. Let  $r$  = the correlation between  $t_f$  and  $t_s$ , estimated by the ratio of SDs of the treatment effect estimates in the full group and subgroup.
4. Let  $p_{inter}$  be the p-value from the test of the intersection hypothesis using Dunnett's test; specifically,  $p_{inter} = 1 - \text{probnorm}(t_{max}, t_{max}, r)$ .

Then, if  $p_{inter} < 0.025$  and either  $p_f < 0.025$  or  $p_s < 0.025$  (with treatment effect favoring CAP-1002), the test of treatment effect for the primary efficacy endpoint will be considered statistically significant.

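### The single missing-not-at-random analysis of the primary endpoint is incompletely specified, and imputing only from subjects with a new ICD may leave too few donors for a stable or directed test

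*SAP*

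**What the plan says.** SAP section 9 uses maximum likelihood for the mITT analysis and multiple imputation from all observations for the ITT analysis, both under missing at random (MAR). It then accepts that MAR cannot be tested and that "it seems possible that subjects with poorer outcome may be more likely to miss trial assessments". In response it plans, at the final analysis only, a pattern-mixture multiple imputation in which "the imputation will be based on a pre-specified subset of subjects". The next sentence should define the subset but is a fragment: for this analysis, "only those subjects who had implantable cardioverter defibrillators (ICDs) inserted during the trial".

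The SAP gives no reason for choosing ICD recipients, no analysis population for this analysis, no minimum donor number, no fallback, and no range of departures from MAR. The imputation model is described only for the ITT analysis ("Variables in the imputer's model will be baseline observation", then the Month 6 change, the Month 12 change and treatment group) and is not restated here. On the number of imputations: "Because very few missing observations are expected in this trial, 5 imputed data sets will be used for all analyses using multiple imputation".

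Protocol 6.9, 7.3.5 and 7.3.6 allow MRI after a device is placed during the study, provided the imaging site is trained and certified for it. Otherwise: "If subjects develop MRI contraindications, a cardiac MRI will not be performed". Such subjects stay in follow-up.

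**The concern.** A donor-based imputation needs donors with the value being imputed. A subject with a new ICD loses the follow-up MRI if the site is not certified or the device is a contraindication. Protocol 4.3, exclusion 9, shows that both are foreseen at entry: it provides for uncertified sites and lists device features that rule MRI out, such as recently implanted leads and subcutaneous ICDs. Donors may therefore lack infarct size at Month 6, Month 12 or both.

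Nothing fixes the direction of the departure either. If the stated imputation variables carry over, treatment group is in the model. With a handful of donors, the donor-based treatment difference could by chance exceed the MAR one, and the check would then favor CAP-1002.

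Other routes to a missing primary endpoint, such as withdrawal, death, or a fall in GFR that prevents contrast, are not represented by ICD recipients who did have MRI. At stake is whether the primary result gets a usable test against informative missingness.

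**Working it through.** **The plan's own figures.** The Protocol synopsis randomizes 103 "to achieve up to 93 subjects with complete 12 month data (assumes 10% non-completion rate and 103 subjects randomized"): 103 × (1 − 0.10) = 92.7, which reproduces 93. That implies about 10 subjects without complete data, which sits uneasily with the SAP's expectation of very few missing observations. The stated power of more than 90% at N = 100 is also consistent with a simulation of the closed test (0.999).

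**Inputs from the documents.** CAP-1002 arm 69 ("n=14 Safety Cohort, n=69 Primary Randomized Cohort"); placebo about 34; SD 10 (Protocol Table 4). Imputation variables as in the ITT analysis, assumed to carry over.

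**Inputs assumed, because the documents give neither.** p = share of subjects with an ICD inserted during the trial, 3-20%. m = share of those with both follow-up MRIs, 30-90%.

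**Donor count.** With q = p × m, CAP-1002 donors A ~ Binomial(69, q) and placebo donors B ~ Binomial(34, q). Expected donors = 103q. A Month 12 regression on intercept, treatment, baseline and Month 6 has 4 coefficients. One residual degree of freedom then needs 5 complete donors, with at least one per arm:

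P(fit) = P(A + B ≥ 5, A ≥ 1, B ≥ 1).

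Each cell shows expected donors, then P(fit):

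| ICD rate | m = 30% | m = 50% | m = 70% | m = 90% |
|---|---|---|---|---|
| 3% | 0.9; 0.00 | 1.5; 0.02 | 2.2; 0.06 | 2.8; 0.13 |
| 5% | 1.5; 0.02 | 2.6; 0.10 | 3.6; 0.26 | 4.6; 0.45 |
| 10% | 3.1; 0.18 | 5.2; 0.54 | 7.2; 0.81 | 9.3; 0.93 |
| 15% | 4.6; 0.45 | 7.7; 0.85 | 10.8; 0.97 | 13.9; 0.99 |
| 20% | 6.2; 0.70 | 10.3; 0.96 | 14.4; 0.99 | 18.5; 1.00 |

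At 10% and 50%, q = 0.05. Expected donors are 69 × 0.05 = 3.5 CAP-1002 and 34 × 0.05 = 1.7 placebo, and the chance of no placebo donor is 0.95^34 = 0.17. Taking 5-10% ICD with half scanned gives about 3 to 5 donors, so 3 − 4 = −1 to 5 − 4 = 1 residual degrees of freedom.

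**Recent MI subgroup.** The closed test also uses this subgroup, but stratum is not among the stated imputation variables. If imputation were done within Recent MI (about 52 subjects), the chance of 5 or more donors at a 10% ICD rate would be 0.02-0.51.

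**Precision when the model does fit.** Ignoring covariates, the SE of the treatment coefficient is 10 × √(1/a + 1/b) for a CAP-1002 and b placebo donors:

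- 4 + 2 donors: 8.7 points
- 7 + 3 donors: 6.9 points
- whole trial, 62 + 31 completers: 2.2 points

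Only 5 imputed data sets are planned.

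**The case against.** The defining sentence is broken, so treating ICD recipients as donors is an inference. It could instead mean that only the missing values of ICD recipients are handled as not at random. The sentence before it makes the donor reading the more natural one, but what the text itself proves is an incomplete specification.

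A reader might infer that ICD recipients are a tiny group with the least follow-up MRI and that the analysis is probably not estimable. The documents do not support this. They give no rates, they expressly allow MRI at certified sites, and an ICD placed after Month 6 leaves the Month 6 scan intact. The four-coefficient model is carried over from the ITT analysis, and under fully conditional specification a donor with one visit missing can still inform the other visit's model. In the table the model usually fits at ICD rates of 15-20%.

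A reader might also infer that the analysis does not address the stated worry at all. That goes too far: receiving an ICD is a plausible marker of poorer outcome, and imputing from such a subset is a recognised pattern-mixture approach.

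The consequence is bounded. This is a sensitivity analysis outside the success rule. With equal strata the planned full-group effect is (14.70 + 7.35)/2 = 11.0 points; if 10% are missing with no treatment difference it falls to 11.025 × 0.90 = 9.9.

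These points remove the stronger readings. They do not supply the missing specification, a minimum donor count, a fallback or a controlled direction. The small drop to 9.9 also rests on planning effects taken from the 14-subject open-label Safety Cohort and CADUCEUS; the check matters most if the observed effect is smaller.

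**Conclusion.** The point holds as a weakness of specification and method that is cheap to improve. It is not a demonstration that the analysis will fail.

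On the natural reading, the only departure from MAR planned for the primary endpoint depends on a donor group whose size neither document gives. It may be non-estimable or very unstable: fit is unlikely at ICD rates of 5% or less (0.00-0.45), uncertain at 10% (0.18-0.93), and usual at 15-20% unless few donors have MRI. These figures rest on assumed ICD and MRI rates and on the ITT imputation variables carrying over. Even when it runs, it examines one scenario and does not ensure that imputed CAP-1002 values are less favorable than under MAR. The SAP's concern is therefore tested weakly. The primary analysis and its success rule are not affected.

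**What to change.** Complete the sentence: say whose values are imputed, from whom and why, in which population and with which model.

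Make the main analysis a delta-adjusted multiple imputation. Impute under MAR with treatment, stratum, baseline and Month 6 in the model. Enter stratum as a covariate rather than imputing within arm and stratum, because 34/2 = about 17 placebo subjects per stratum is a small cell. Then worsen the imputed CAP-1002 values in steps until significance is lost, and report that tipping point for both the full-group and the Recent MI test. This does not depend on the number of ICD recipients.

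The ICD-based imputation can stay as a supplementary scenario, with a pre-stated minimum number of donors per arm and a fallback if it is not met.

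The cost is SAP wording, some standard programming and one more table, with no new data. It should be settled before database lock.

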9.2 Determination of Sample Size

In total, a maximum of approximately one hundred thirty-four (134) subjects with a MI and resulting ischemic left ventricular dysfunction meeting all inclusion and no exclusion criteria will be enrolled. The first fourteen (14) subjects (7 Recent MI and 7 Chronic MI) will receive CAP-1002 open-label and will be designated as the Safety Cohort. The approximate maximums of one hundred three (103) subjects in the Primary Randomized Cohort (51-52 Recent MI and 51-52 Chronic MI) and the up to 17 subjects in the Exploratory Randomized Cohort will begin to enroll only after DSMB review of the Safety Cohort data and recommendation to proceed. These approximately 120 subjects in the Primary Randomized Cohort and Exploratory Randomized Cohort will be independently randomized in a double-blind fashion to receive either CAP-1002 or placebo in a 2:1 ratio, favoring CAP-1002 to achieve approximately up to 93 subjects with complete 12 month data in the Randomized Cohort. A balancing algorithm will be used to ensure site-specific balancing to the 2:1 allocation after stratifying for prior MI.

The Safety Cohort was evaluated once all subjects reached the primary safety endpoint assessed at the 1 month visit. With n=14, if no significant safety events are observed, the one-sided 95% upper bound for the true rate of significant events would be < 20%. The DSMB conducted a review of the Safety Cohort data and made a recommendation to proceed with randomization of the next 120 subjects. Efficacy and safety will be assessed at all post-screening visits, although

MRI testing will only be completed at 6 and 12 months; the 12 month visit is the primary efficacy endpoint.

Historical Data

The CADUCEUS and ALLSTAR Safety Cohort data provide some background for planning sample size to test for efficacy. The efficacy endpoints in the CADUCEUS study and in the ALLSTAR Safety Cohort included the relative change in the Month 6 and 12 outcomes relative to baseline as judged by MRI assessment of infarct size (measured in %). Assumptions used for power calculations are summarized below in [Table 4](#) with the relative change displayed as a percent improvement from baseline. The ALLSTAR Safety Cohort was used for the assumed means and SDs and CADUCEUS was used for the treatment effect in Chronic MI patients relative to Recent MI.

Table 4. Sample Size Assumptions

| | Month 6 | | Month 12 | |
|------------------|---------|-------|----------|-------|

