### 2.3.5 Primary Efficacy Hypothesis

The primary efficacy hypothesis is that CAP-1002 is superior to placebo in reducing infarct size in either all subjects combined (“full group”) or in subjects with recent MI (“subgroup”). A closed testing procedure will be used so that strong control of type 1 error is maintained. Specifically, the following hypothesis sets will be tested:

$$1) \quad H_{0,s}: \mu_{c,s} - \mu_{p,s} = 0 \quad \text{or} \quad H_{0,f}: \mu_{c,f} - \mu_{p,f} = 0 \\ H_{a,s}: \mu_{c,s} - \mu_{p,s} < 0 \quad H_{a,f}: \mu_{c,f} - \mu_{p,f} < 0$$

and

$$2) \quad H_{0,s} \cap H_{0,f}: \mu_{c,s} - \mu_{p,s} = 0 \text{ and } \mu_{c,f} - \mu_{p,f} = 0 \\ H_{a,s} \cap H_{a,f}: \mu_{c,s} - \mu_{p,s} < 0 \text{ or } \mu_{c,f} - \mu_{p,f} < 0$$

where  $s$  denotes the subgroup,  $f$  denotes the full group,  $\mu_{c,s}$  and  $\mu_{p,s}$  are mean percent changes in the CAP-1002 and placebo treatment groups, respectively, in the subgroup, and  $\mu_{c,f}$  and  $\mu_{p,f}$  are mean percent changes in the CAP-1002 and placebo treatment groups, respectively, in the full group.

Therefore, both the intersection null hypothesis ( $H_{0,s} \cap H_{0,f}$ ) and either of the individual null hypotheses ( $H_{0,s}$  or  $H_{0,f}$ ) must be rejected at the (one-sided) 0.025 significance level for the trial to be declared a success. In other words, the null hypothesis of “no treatment effect in the full group and no treatment effect in the recent MI subgroup” must be rejected at the one-side 0.025 significance level, necessarily meaning that either the result is significant in the full group, in the recent MI subgroup, or both. The results of the tests of the individual hypotheses (also at the one-sided 0.025 significance level) determines which specific comparisons are significant.

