## 9. EFFICACY ANALYSIS

All efficacy parameters will be listed for the primary ITT population and summarized for the mITT population. The primary analysis of primary and secondary efficacy endpoints will be done using the primary mITT population. Secondary analyses may be done using the other analysis populations defined in [Section 6](#) or in subgroups defined in [Section 7.4](#). In addition, “last observation” analyses will be done for certain parameters for which some subjects’ final assessments were done too late to be included in the Month 12 analysis window.

Analyses of changes from baseline will be done using general linear models with baseline values as covariates. Analyses of the effect of treatment group, analysis window (e.g., baseline, Month 6, Month 12), and their interaction will be done using mixed effects linear regression, with subject as a random effect, analysis window, and treatment group as fixed effects, and baseline as a fixed-effect covariate. For “last observation” analyses, “time” as a continuous covariate will be substituted for analysis window. Study site may also be included as a random effect if there is evidence of correlation within study sites (per the interclass correlation coefficient from the unconditional model) and/or if doing so appreciably improves the model fit (e.g., per Akaike’s Information Criterion). Other covariates that may be considered include age (< 65 vs.  $\geq$  65 years), sex, race (African-American vs. other), baseline 6MWT, baseline LVESV, baseline NT-proBNP, and DSA (as an indicator variable). Residuals will be evaluated for substantial departure from normality and independent and constant variance and appropriate remedies (e.g., data transformations, detecting and assessing the influence of outliers, alternative analytical approaches) will be attempted when necessary. An unstructured covariance will be the default covariance structure but other structures (e.g., compound symmetry) may be used to evaluate sensitivity to the choice of structure or, if study site is included as a random effect, to achieve convergence.

Assuming missing observations are “missing at random” (MAR), i.e., the fact that they are missing is unrelated to the missing variable but can be related to another variable on which data have been collected, the maximum likelihood (ML) approach is able to handle subjects with

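### The closed test's correlation formula is exact for the planned model only if Recent and Chronic MI outcomes vary equally; the SAP does not state this condition and has no fallback when the formula gives 1 or more

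*SAP*

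**What the plan says.** SAP 2.3.5 states: "A closed testing procedure will be used so that strong control of type 1 error is maintained". It adds that the joint null "must be rejected at the one-side 0.025 significance level, necessarily meaning" that at least one of the two individual comparisons, full group or Recent MI, is significant.

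SAP section 9 gives the mechanics. Step 3 sets r, the correlation of the two t-statistics, to a value "estimated by the ratio of SDs of the treatment effect estimates in the full group and subgroup", that is, r = SE_full / SE_Recent. Step 4 lets p_inter "be the p-value from the test of the intersection hypothesis using Dunnett's test", calculated as one minus the bivariate normal probability that both statistics lie below the larger observed one, with correlation r. If p_inter and at least one individual p-value are below 0.025, with the effect favouring CAP-1002, "the test of treatment effect for the primary efficacy endpoint will be considered statistically significant".

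The model in the same section has analysis window and "treatment group as fixed effects, and baseline as a fixed-effect covariate", with subject random. "An unstructured covariance will be the default covariance structure", but nothing lets it differ between Recent and Chronic MI. On planning values, Protocol 9.2 says: "The ALLSTAR Safety Cohort was used for the assumed means and SDs". Protocol Table 4 and SAP Table 1 show SD 10.00 in every cell.

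**The concern.** The Recent MI subjects are part of the full group, so the two statistics are correlated and the intersection cut-off depends on how strongly. A ratio of standard errors equals that correlation only under a particular weighting of the strata. With the planned model, that requires equal outcome variance in Recent and Chronic MI.

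If Chronic MI varies more, the formula gives too high an r and too low a cut-off for the test that decides trial success. If the ratio reaches 1, the bivariate normal in step 4 no longer yields a p-value. The error guarantee therefore rests on a nuisance condition that the SAP does not mention. The problem does not shrink with sample size.

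**Working it through.** **Inputs**
- One-sided level 0.025 (SAP 2.3.5); r and p_inter from steps 3 and 4 (SAP section 9).
- About 51-52 subjects per stratum (Protocol 9.2), randomized 2:1 within stratum (SAP section 5). The Recent share of the full-group estimate, w, is therefore about 0.5.
- SD 10 in both strata (Protocol Table 4, SAP Table 1).
- k = Chronic SD / Recent SD. The documents give only k = 1. Other values are assumptions, shown from 0.5 to 2.0.

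**Formula**
Write the full-group estimate as w × Recent + (1 − w) × Chronic, with the strata independent. Then:
- SE_f² = w² SE_s² + (1 − w)² SE_c²
- covariance of full-group and Recent estimates = w SE_s²
- true correlation = w SE_s / SE_f
- SAP value: r = SE_f / SE_s

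At w = 0.5, SE_c = k SE_s, so SAP r = 0.5√(1 + k²) and true correlation = 1/√(1 + k²). They are equal only at k = 1. SAP r reaches 1 at k = √3 = 1.73.

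**The plan's own case**
At k = 1 both expressions are 0.7071, the cut-off is 2.178 and the error is 2.50%. With equal SDs and w = 0.3, 0.4 or 0.6, the error is also 2.50%. The plan's figure is reproduced.

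**Other SD ratios, large samples**
The cut-off is solved at the SAP's r. The error is then evaluated at the true correlation.

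| k | SAP r | true correlation | cut-off, SAP r | cut-off, true | error |
|---|---|---|---|---|---|
| 0.5 | 0.559 | 0.894 | 2.205 | 2.111 | 2.0% |
| 1.0 | 0.707 | 0.707 | 2.178 | 2.178 | 2.5% |
| 1.2 | 0.781 | 0.640 | 2.159 | 2.192 | 2.7% |
| 1.25 | 0.800 | 0.625 | 2.152 | 2.195 | 2.8% |
| 1.5 | 0.901 | 0.555 | 2.107 | 2.205 | 3.2% |
| 1.7 | 0.986 | 0.507 | 2.022 | 2.211 | 3.9% |

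**Simulation at the planned size**
Null trials with 46 Recent (31:15) and 47 Chronic (31:16) completers; the split of the 93 is assumed. The full success rule was applied. The SAP does not say what to do when r is 1 or more, so r was first capped at 1.

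| k | SAP r, capped at 1 | correct r |
|---|---|---|
| 1.0 | about 2.9% | 2.8-2.9% |
| 1.25 | about 3.2% | 2.8-2.9% |
| 1.5 | about 3.8% | 2.8-2.9% |
| 2.0 | about 4.5% | 2.8-2.9% |

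Repeat runs differ by about 0.1 percentage point. The excess over 2.5% that remains with the correct r comes from referring t-statistics to a normal distribution, which is a separate matter.

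The estimated r is 1 or more in about 15% of trials at k = 1.5 and about 80% at k = 2.0. If those trials are counted as non-significant instead of capped, the error is about 2.8% at k = 1.5 and 0.6% at k = 2.0.

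**How firmly do the documents support k = 1?**
The SDs come from 14 open-label subjects, 7 per stratum (Protocol 9.2). Suppose the two observed SDs had been identical. The 95% interval for the true SD ratio, from F on 6 and 6 degrees of freedom with normal data, would still be about 0.41 to 2.41. The source data can neither establish nor refute equality.

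**The case against.** A reader might infer that type I error control fails in this trial, or that the primary test runs at nearly 5%. The documents do not support that.

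- The formula is exact under the plan's own SDs, and nothing in the documents says that Chronic MI varies more. If it varies less, the test is conservative. This stands.
- The highest error figures need k near 2 and a cap on r that the SAP does not contain. Without the cap, large k gives trials with no computable p-value, not many false positives. This also stands.
- At modest differences the effect is small: 2.6% at k = 1.1 and 2.7% at k = 1.2. It arises only when both nulls are true, because each individual hypothesis is still tested at 0.025. This stands.
- The ratio is not wrong for every model. If the full-group estimate were weighted by inverse stratum variance, then w = SE_f²/SE_s², so w SE_s/SE_f = SE_f/SE_s and the SAP's r would be correct. The residual check in SAP section 9 could lead there, since it looks at constant variance and allows other analytical approaches. It is only a partial safeguard: the remedy is left open, would be chosen after seeing the data, and is not linked to r.
- The correct r is not a direct output of the planned model. The weight w, or a joint covariance, has to be specified. This stands and is counted in the cost.

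**Conclusion.** The concern holds as a conditional one. For the planned full-group model, step 3 is correct only under equal stratum variances, and the SAP promises strong control without saying so. If Chronic MI is more variable, the large-sample error rises to 2.8% at k = 1.25, 3.2% at 1.5 and 3.9% at 1.7. If it is less variable, the error falls, to 2.0% at k = 0.5. These figures assume w of about 0.5 and an SD ratio for which the documents give no evidence either way. At large k the main defect is a primary p-value that cannot be computed, with no rule for that case. The change is worth making because it concerns the test that decides success and is cheap. It does not show that the planned analysis is invalid under its stated assumptions.

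**What to change.** In step 3, define r as the estimated covariance of the full-group and Recent Month 12 effect estimates divided by the product of their standard errors, with variances allowed to differ by stratum. An adequate approximation is

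r = w SE_s / √(w² SE_s² + (1 − w)² SE_c²).

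Here SE_s comes from the Recent fit and SE_c from a Chronic-stratum fit. Fix w in advance, for example as the Recent share of subjects analysed.

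This r is always below 1, so p_inter can always be computed. Under equal SDs it reduces to the present formula. In large samples it gives 2.5% at every k examined.

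The cost is one additional Chronic fit, or a joint covariance step, and a short SAP edit, with no new data and no change in sample size. The cut-off becomes slightly stricter if Chronic MI varies more (2.205 instead of 2.107 at k = 1.5) and slightly more lenient if it varies less (2.111 instead of 2.205 at k = 0.5).
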